10.1.2.2 Full Analysis Set

The full analysis set includes all subjects who received blinatumomab.

10.1.2.3 Pharmacokinetic Analysis Set

The pharmacokinetic analysis set includes all subjects who received any infusion of blinatumomab **or** pembrolizumab and have at least 1 pharmacokinetic sample collected.

10.1.2.4 Pharmacodynamic Analysis Set

The pharmacodynamic analysis set includes all subjects who receive any infusion of blinatumomab and have at least 1 pharmacodynamic sample collected.

10.1.3 Subgroups

- Sex (male vs female)
- Race/ethnicity (categories depend on the data, all races with less than 5% of the total enrolled subjects will be pooled together for summary purposes)
- Age group (< 65 vs ≥ 65 and < 75 vs ≥ 75 years old)
- Region (North America, Europe, and rest of the world [ROW]). If any region has small number of subjects, it will be combined with other regions)
- Additional subgroups may be explored, including but not limited to:
 - Number of prior salvage therapies (0 vs 1 vs ≥ 2)
 - B:T cell ratio at baseline
 - PD-L1 positivity

10.1.4 Handling of Missing and Incomplete Data

Subjects without tumor response assessments will be considered as non-responders. Otherwise, only non-missing data will be analyzed. No other missing value replacement procedure will be deployed for clinical data.

10.2 Sample Size Considerations

Part 1

A rolling 6 dose design will be used. An additional 4 subjects per cohort can be enrolled to further evaluate safety and PK data if needed. There will be a minimum of 6 subjects and a maximum of 30 subjects enrolled.

Part 2

Forty subjects will be enrolled in Part 2. With 40 subjects, the 95% exact confidence interval (Clopper and Pearson, 1934) for the estimate of ORR can be calculated. The 95% confidence intervals for some ORRs are shown in the table below.

Table 10-1. Estimated 95% Confidence Interval for ORR

ORR	95% Confidence Interval
0.40	(0.25, 0.57)
0.45	(0.29, 0.61)
0.50	(0.34, 0.71)
0.55	(0.38, 0.71)
0.60	(0.43, 0.75)

ORR = objective response rate

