For part 2, the dosing will be determined based on the safety of the combination of blinatumomab and pembrolizumab and the MTD of blinatumomab established in part 1 per DLRT. For part 2, the DLT observation period will be determined by the cohort chosen in part 1 for the part 2 expansion. Part 2 will consist of an expansion cohort to collect further safety and PK data as well as provide a preliminary estimate of the efficacy of the combination of blinatumomab and pembrolizumab. Dose limiting toxicities and efficacy will be monitored by the Data Review Team (DRT) to ensure they do not reach a pre-defined threshold of 25%. If this threshold is reached, the DRT will have the discretion to change to another dose/schedule tested in phase 1b part 1 based on the totality of the available data. The details of DLT boundaries are provided in Section [10.3.1](#).

The study endpoints are defined in Section [10.1.1](#).

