10.3 Planned Analyses

10.3.1 Interim Analyses

DRT will conduct evaluations of efficacy for ORR by the Lugano Classification (Cheson et al, 2014) during the first 12 weeks since starting blinatumomab and safety for DLT rate to assess if the threshold for early trial termination has been reached.

Table 10-2 shows the efficacy stopping rules using a Bayesian approach to potentially terminate the study if the posterior probability that ORR is less than 50% is $> 80\%$. The stopping boundaries assume a prior beta distribution (1, 1). The operating characteristics in Table 10-3 provide the probability of stopping the trial early for given hypothetical true ORR.

Table 10-2. Efficacy stopping Boundary With Batch Size of 10 Subjects, Posterior Probability of 80% and ORR of 50%

Number of DLT evaluable subjects	Stop study if observing these many DLTs
10	≤ 3
20	≤ 8
30	≤ 12
40	Always stop

Table 10-3. Operating Characteristics With Batch Size of 10 Subjects

True ORR	Prob of Stopping Early	Average Sample Size
0.40	70%	23
0.45	52%	27
0.50	34%	32
0.55	19%	19
0.60	9%	38

Table 10-4 shows the safety stopping rules using a Bayesian approach to terminate the study if the posterior probability that the DLT rate is greater than 25% is $> 90\%$. The stopping boundaries assume a prior beta distribution (0.50, 1.50). The evaluations could occur more frequently if necessary to address emerging safety concerns. The operating characteristics in Table 10-5 provide the probability of stopping the trial early for given hypothetical true DLT rates.

Table 10-4. Safety Stopping Boundary With Batch Size of 10 Subjects, Posterior Probability of 90% and DLT Limit of 25%

Number of DLT evaluable subjects	Stop study if observing these many DLTs
10	≥ 5
20	≥ 8
30	≥ 11
40	Always stop

DLT = dose limiting toxicity

Table 10-5. Operating Characteristics With Batch Size of 10 Subjects

True DLT Rate	Prob of Stopping Early	Average Sample Size
0.20	6%	38
0.25	17%	36
0.30	36%	32
0.35	57%	27
0.40	76%	22

DLT = dose limiting toxicity; prob = probability

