8.1 Interim Analyses

DRT will conduct evaluations of efficacy for ORR by the Lugano Classification (Cheson et al, 2014) during the first 12 weeks since starting blinatumomab and safety for DLT rate to assess if the threshold for early trial termination has been reached.

Table 2 shows the efficacy stopping rules using a Bayesian approach to potentially terminate the study if the posterior probability that ORR is less than 50% is $> 80\%$. The stopping boundaries assume a prior beta distribution (1, 1). The operating characteristics in Table 3 provide the probability of stopping the trial early for given hypothetical true ORR.

Table 2. Efficacy Stopping Boundary With Batch Size of 10 Subjects, Posterior Probability of 80% and ORR of 50%

Number of evaluable subjects	Stop study if observing these many responders
10	≤ 3
20	≤ 8
30	≤ 12
40	Always stop

Table 3. Operating Characteristics With Batch Size of 10 Subjects

True ORR	Prob of Stopping Early	Average Sample Size
0.40	70%	23
0.45	52%	27
0.50	34%	32
0.55	19%	19
0.60	9%	38

Table 4 shows the safety stopping rules using a Bayesian approach to terminate the study if the posterior probability that the DLT rate is greater than 25% is > 90%. The stopping boundaries assume a prior beta distribution (0.50, 1.50). The evaluations could occur more frequently if necessary, to address emerging safety concerns. The operating characteristics in Table 5 provide the probability of stopping the trial early for given hypothetical true DLT rates.

Table 4. Safety Stopping Boundary With Batch Size of 10 Subjects, Posterior Probability of 90% and DLT Limit of 25%

Number of DLT evaluable subjects	Stop study if observing these many DLTs
10	≥ 5
20	≥ 8
30	≥ 11
40	Always stop

DLT = dose limiting toxicity

Table 5. Operating Characteristics With Batch Size of 10 Subjects

True DLT Rate	Prob. of Stopping Early	Average Sample Size
0.20	6%	38
0.25	17%	36
0.30	36%	32
0.35	57%	27
0.40	76%	22

DLT = dose limiting toxicity; prob = probability

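### Two figures in the Part 2 planning tables cannot be reproduced (upper confidence limit at ORR 0.50, average sample size at ORR 0.55), and the protocol labels its efficacy rule in DLTs

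*Protocol*

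**What the plan says.** **Precision.** Protocol section 10.2 fixes Part 2 at 40 subjects and states: "With 40 subjects, the 95% exact confidence interval (Clopper and Pearson, 1934) for the estimate of ORR can be calculated". It then says "The 95% confidence intervals for some ORRs are shown in the table below". The row for ORR 0.50 in Table 10-1 reads 0.34 to 0.71, and the row for 0.55 reads 0.38 to 0.71. SAP section 3.2, Table 1, carries the same values.

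**Operating characteristics of the efficacy rule.** Protocol section 10.3.1 says "The operating characteristics in Table 10-3 provide the probability of stopping the trial early for given hypothetical true ORR"; SAP section 8.1 says "The operating characteristics in Table 3 provide the probability of stopping the trial early for given hypothetical true ORR". Down the rows for ORR 0.40 to 0.60, both tables list average sample sizes of 23, 27, 32, 19 and 38. The entry of 19 is at ORR 0.55, next to a 19% probability of stopping early.

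**Heading of the efficacy boundary.** Protocol Table 10-2 is titled as the efficacy boundary for an ORR of 50%, but its first column counts DLT-evaluable subjects and its second is headed "Stop study if observing these many DLTs". SAP Table 2 prints the same cut-offs and counts responders.

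**Thresholds.** Protocol section 3.1 (Part 2) says that dose limiting toxicities and "efficacy will be monitored by the Data Review Team (DRT) to ensure they do not reach a pre-defined threshold of 25"%. Protocol section 3.5.1, the Figure 1 legend and SAP section 3.1 (Part 2 text and Figure 1 legend) say the same. The protocol synopsis, protocol section 10.3.1 and SAP section 8.1 use 25% for the DLT rate and 50% for ORR.

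**The concern.** An exact binomial interval at an observed proportion of one half must be symmetric about 0.5, and 0.34 to 0.71 is not. The average sample size should rise steadily as the true ORR rises, because futility stopping becomes rarer; a fall from 32 to 19 followed by a rise to 38 breaks that order.

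Table 10-1 is the only statement of what 40 subjects buy in precision, and Table 10-3 is the only description of how the futility rule behaves. Table 10-2 is the boundary set out in the protocol for the Data Review Team's efficacy evaluation. Read literally, its heading stops the study for 3 or fewer DLTs in 10 subjects, that is, when toxicity is low. The shared 25% wording, read literally, sets a ceiling that efficacy must not reach.

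**Working it through.** **Inputs.** n = 40 and two-sided 95% Clopper-Pearson limits (protocol 10.2). Beta(1, 1) prior, looks every 10 subjects, stop if Pr(ORR < 50%) > 80%, boundaries ≤3/10, ≤8/20, ≤12/30, maximum 40 (protocol 10.3.1, SAP 8.1).

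**1. Confidence intervals.** For x responders of n, the lower limit is the 0.025 quantile of Beta(x, n − x + 1) and the upper limit is the 0.975 quantile of Beta(x + 1, n − x).

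| ORR | x/40 | Printed | Computed |
|---|---|---|---|
| 0.40 | 16 | 0.25, 0.57 | 0.2486, 0.5667 |
| 0.45 | 18 | 0.29, 0.61 | 0.2926, 0.6151 |
| 0.50 | 20 | 0.34, **0.71** | 0.3380, **0.6620** |
| 0.55 | 22 | 0.38, 0.71 | 0.3849, 0.7074 |
| 0.60 | 24 | 0.43, 0.75 | 0.4333, 0.7514 |

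At ORR 0.50 the lower limit reproduces and the upper does not. Other methods at 20/40 do not give the printed pair either: Wald 0.345 to 0.655, Wilson 0.352 to 0.648, exact 90% 0.361 to 0.639, exact 99% 0.295 to 0.705. No x/n with n from 10 to 59 has an exact 95% interval that rounds to 0.34, 0.71. The printed width is 0.71 − 0.34 = 0.37; the correct width is 0.66 − 0.34 = 0.32. The upper limit at ORR 0.45 should round to 0.62 rather than 0.61, a difference in the last digit only.

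**2. Efficacy boundaries.** With the Beta(1, 1) prior, Pr(ORR < 50%) is 0.8867 at 3/10 and 0.7256 at 4/10; 0.8083 at 8/20 and 0.6682 at 9/20; 0.8595 at 12/30 and 0.7634 at 13/30. The printed cut-offs of 3, 8 and 12 are therefore right.

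**3. Operating characteristics**, by exact binomial recursion through the looks at 10, 20 and 30:

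| True ORR | Printed stop / average N | Computed stop / average N |
|---|---|---|
| 0.40 | 70% / 23 | 71.0% / 22.7 |
| 0.45 | 52% / 27 | 52.2% / 27.5 |
| 0.50 | 34% / 32 | 33.7% / 31.9 |
| 0.55 | 19% / **19** | 19.0% / **35.3** |
| 0.60 | 9% / 38 | 9.3% / 37.7 |

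At ORR 0.55 the probabilities of stopping at 10, 20 and 30 are 0.1020, 0.0729 and 0.0147, which sum to 0.1896. The average is 10 × 0.1020 + 20 × 0.0729 + 30 × 0.0147 + 40 × 0.8104 = 1.02 + 1.46 + 0.44 + 32.42 = 35.3.

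The printed row also fails without any model. If 19% stop early, all at the first look, the average is 0.19 × 10 + 0.81 × 40 = 34.3. If all of them stop at the third look, it is 0.19 × 30 + 0.81 × 40 = 38.1. An average of 19 would need an early-stopping probability of at least (40 − 19)/30 = 0.70.

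**4. Safety rule, as a control.** With the stated Beta(0.5, 1.5) prior, the cut-offs of 5, 8 and 11 reproduce. So does protocol Table 10-5, within about one unit: 6.2% / 38.5, 17.4% / 36.1, 35.7% / 32.2, 57.3% / 27.3 and 76.4% / 22.5.

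**5. Headings and thresholds side by side.** The column headings of protocol Table 10-2 are the same as those of the safety table, Table 10-4. One table would stop for 3 or fewer DLTs in 10 and the other for 5 or more. SAP Table 2, with identical cut-offs, is in responders. The shared 25% wording in the design sections cannot describe the same rule as the 50% ORR threshold in 10.3.1.

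**The case against.** The strongest reply concerns weight. Everything here describes Part 2, and SAP section 11 records the decision not to run it. The choice of 40 subjects is not derived from either wrong cell, and no decision depends on the average sample size column. The 19% in the faulty row is right, and so are all the boundaries. Both errors look like copying slips: 0.71 repeats the row below, and 19 repeats the adjacent percentage. The title of Table 10-2 and the sentence introducing it make clear that ORR is meant. The 25% passage in protocol 3.1 goes on to refer to DLT boundaries in 10.3.1, so a reader would attach 25% to DLTs. The Data Review Team's working procedures are in a charter that is not among these documents.

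Most of this stands as a limit on consequence. It does not make the figures right. The two wrong cells appear in both documents, so they are not a fault of one file. SAP section 11 changes the timing of the primary analysis but does not withdraw these tables. Context shows what the heading and the 25% wording were meant to say; the text itself says something else, and the protocol and SAP disagree on what Table 10-2 counts.

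**Conclusion.** The concern holds. At ORR 0.50 the upper confidence limit is overstated by 0.05 (0.71 printed, 0.66 correct). At ORR 0.55 the average sample size is understated by 16 subjects (19 printed, 35 correct), and the printed value is incompatible with the stopping probability beside it. The DLT heading on Table 10-2 is wrong in the protocol only. The wording that joins the 25% limit to efficacy is in both documents and conflicts with the 50% ORR threshold stated elsewhere in each.

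The calculations assume the documents' own inputs: exact Clopper-Pearson limits at n = 40, looks at 10, 20 and 30, a maximum of 40, and the printed boundaries. Since Part 2 will not proceed, no trial result is affected. What is wrong is the stated precision and operating characteristics of the design.

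**What to change.** - Protocol Table 10-1 and SAP Table 1: at ORR 0.50, print (0.34, 0.66). In the same edit, change the upper limit at ORR 0.45 from 0.61 to 0.62.
- Protocol Table 10-3 and SAP Table 3: at ORR 0.55, print an average sample size of 35.
- Protocol Table 10-2: head the columns in evaluable subjects and responders, matching SAP Table 2.
- Protocol sections 3.1 and 3.5.1 and the Figure 1 legend, and SAP section 3.1 with its Figure 1 legend: state the 25% DLT limit and the 50% ORR futility threshold in separate sentences, consistent with protocol 10.3.1.

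Alternatively, since Part 2 was dropped, add a line to SAP section 11 marking the Part 2 precision and stopping tables as not applicable. Either route is a text correction, with no change to data, analyses or sample size.

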10.3 Planned Analyses

10.3.1 Interim Analyses

DRT will conduct evaluations of efficacy for ORR by the Lugano Classification (Cheson et al, 2014) during the first 12 weeks since starting blinatumomab and safety for DLT rate to assess if the threshold for early trial termination has been reached.

Table 10-2 shows the efficacy stopping rules using a Bayesian approach to potentially terminate the study if the posterior probability that ORR is less than 50% is $> 80\%$. The stopping boundaries assume a prior beta distribution (1, 1). The operating characteristics in Table 10-3 provide the probability of stopping the trial early for given hypothetical true ORR.

Table 10-2. Efficacy stopping Boundary With Batch Size of 10 Subjects, Posterior Probability of 80% and ORR of 50%

Number of DLT evaluable subjects	Stop study if observing these many DLTs
10	≤ 3
20	≤ 8
30	≤ 12
40	Always stop

Table 10-3. Operating Characteristics With Batch Size of 10 Subjects

True ORR	Prob of Stopping Early	Average Sample Size
0.40	70%	23
0.45	52%	27
0.50	34%	32
0.55	19%	19
0.60	9%	38

Table 10-4 shows the safety stopping rules using a Bayesian approach to terminate the study if the posterior probability that the DLT rate is greater than 25% is $> 90\%$. The stopping boundaries assume a prior beta distribution (0.50, 1.50). The evaluations could occur more frequently if necessary to address emerging safety concerns. The operating characteristics in Table 10-5 provide the probability of stopping the trial early for given hypothetical true DLT rates.

Table 10-4. Safety Stopping Boundary With Batch Size of 10 Subjects, Posterior Probability of 90% and DLT Limit of 25%

Number of DLT evaluable subjects	Stop study if observing these many DLTs
10	≥ 5
20	≥ 8
30	≥ 11
40	Always stop

DLT = dose limiting toxicity

Table 10-5. Operating Characteristics With Batch Size of 10 Subjects

True DLT Rate	Prob of Stopping Early	Average Sample Size
0.20	6%	38
0.25	17%	36
0.30	36%	32
0.35	57%	27
0.40	76%	22

DLT = dose limiting toxicity; prob = probability

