10.3.2 Dose Level Review Team and Data Review Team (DRT)

10.3.2.1 Dose Level Review Team

A DLRT will review safety data from each cohort in part 1 to recommend if blinatumomab and pembrolizumab in combination is safe and tolerable as defined by DLT criteria and general clinical judgement, taking into account a general benefit risk assessment.

Pharmacokinetic data may be reviewed, if available. Based on the totality of the data, the DLRT may recommend to declare MTD, to escalate to the next dose level, to expand a cohort to a maximum of 10 subjects if the collection of more data is deemed warranted, or to adjudicate the DLT criteria. The DLRT will meet to confirm the decision rules when any of the following criteria are met:

- In 2 or more out of 6 or 3 or more out of 10 subjects, a DLT has been reported in a cohort
- 6 subjects are enrolled in a cohort and all subjects have completed the DLT observation period
- In the event that a cohort is expanded to 10, DLRT will also meet after all subjects have completed DLT observation period

The DLRT will consist of, at minimum, members from the Amgen study team, including at least one clinician, one safety representative, members outside the Amgen study team including, at least one representative of the Merck study team, and one

investigator participating in the study who has recruited subjects into the cohort under review. A cohort may be expanded by DLRT recommendation in the case that the data suggests a change to the anticipated risk/benefit profile, warranting collection of further data at the blinatumomab target dose.

In part 2, DRT will meet after every 10 subjects become DLT evaluable.

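### Protocol Tables 10-3 and 10-5 (SAP Tables 3 and 5) are described as the chance that the trial stops early, but each describes one stopping rule acting alone

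*Protocol*

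**What the plan says.** Protocol Section 10.2 fixes the size of the expansion: "Forty subjects will be enrolled in Part 2". Section 10.3.2.1 fixes the reviews: "In part 2, DRT will meet after every 10 subjects become DLT evaluable". Under Section 10.3.1 the same team looks at the response rate and at "safety for DLT rate to assess if the threshold for early trial termination has been reached".

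The efficacy boundary is at most 3, 8 or 12 responders among 10, 20 or 30 subjects. The safety boundary is at least 5, 8 or 11 DLTs at the same counts.

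Each boundary has its own operating-characteristics table, indexed by one rate only:

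- Efficacy: "The operating characteristics in Table 10-3 provide the probability of stopping the trial early for given hypothetical true ORR".
- Safety: "The operating characteristics in Table 10-5 provide the probability of stopping the trial early for given hypothetical true DLT rates".
- SAP Section 8.1, for its copy of the efficacy table: "The operating characteristics in Table 3 provide the probability of stopping the trial early for given hypothetical true ORR".

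Neither document gives a joint table, says that each table leaves the other rule out, or states an association between response and DLT. The protocol synopsis words the efficacy stop as optional and the safety stop as mandatory. SAP Section 11 records the decision not to go on to Part 2.

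**The concern.** When two rules can each end one trial, the chance of stopping at a given response rate also depends on the DLT rate, and the reverse. A table indexed by one rate alone cannot give a trial-level stopping probability unless the other rule is inactive or ignored. The text claims the trial-level quantity and does not say that the other rule is left out.

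These are the only operating characteristics given for the Part 2 stopping rules. Someone who takes each table at its word will think that a regimen with a good response rate and a DLT rate near the limit is stopped less often, and studied in more subjects, than the two rules together imply.

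**Working it through.** **Inputs**

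- Looks at 10, 20 and 30 subjects, maximum 40 (protocol Sections 10.2, 10.3.1 and 10.3.2.1).
- Efficacy: Beta(1, 1) prior; stop if P(ORR < 50%) > 80%. I count responders, as in the SAP Table 2 column heading; the same column in protocol Table 10-2 is headed as DLTs.
- Safety: Beta(0.50, 1.50) prior; stop if P(DLT rate > 25%) > 90%.
- Association between response and DLT: not given. Assumed independent, then varied.

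**Step 1. Boundaries**

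Posterior probability at the boundary count, with the next milder count in brackets:

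| Look | Efficacy | Safety |
|---|---|---|
| 10 | 3 responders: 0.887 (4: 0.726) | 5 DLTs: 0.935 (4: 0.812) |
| 20 | 8 responders: 0.808 (9: 0.668) | 8 DLTs: 0.913 (7: 0.814) |
| 30 | 12 responders: 0.859 (13: 0.763) | 11 DLTs: 0.908 (10: 0.826) |

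All six printed boundaries are confirmed.

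**Step 2. Each rule alone**

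Let S_k be the probability that the boundary has not been crossed by look k, with S_0 = 1, from an exact binomial recursion. Then P(stop early) = 1 − S_3 and average N = 10 × (S_0 + S_1 + S_2 + S_3).

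| True ORR | Computed | Printed, Table 10-3 |
|---|---|---|
| 0.40 | 70.9%, 22.7 | 70%, 23 |
| 0.45 | 52.2%, 27.5 | 52%, 27 |
| 0.50 | 33.7%, 31.9 | 34%, 32 |
| 0.55 | 19.0%, 35.3 | 19%, 19 |
| 0.60 | 9.2%, 37.7 | 9%, 38 |

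| True DLT rate | Computed | Printed, Table 10-5 |
|---|---|---|
| 0.20 | 6.2%, 38.5 | 6%, 38 |
| 0.25 | 17.4%, 36.1 | 17%, 36 |
| 0.30 | 35.7%, 32.2 | 36%, 32 |
| 0.35 | 57.3%, 27.3 | 57%, 27 |
| 0.40 | 76.4%, 22.5 | 76%, 22 |

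Nine of the ten stopping probabilities agree to rounding; the tenth is 70.9% against 70%. The printed figures are therefore single-rule figures. The one clear misfit is the average N of 19 at ORR 0.55. It also conflicts with the 19% beside it: if 81% of trials reach 40 and the rest stop no earlier than 10, average N is at least 0.81 × 40 + 0.19 × 10 = 34.3.

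**Step 3. Both rules**

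Under independence with common looks, the joint S_k is the product of the two single-rule values (products taken before rounding).

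| | S_1 | S_2 | S_3 |
|---|---|---|---|
| Efficacy, ORR 0.60 | 0.9452 | 0.9123 | 0.9075 |
| Safety, DLT rate 0.20 | 0.9672 | 0.9478 | 0.9377 |
| Joint | 0.9142 | 0.8646 | 0.8510 |
| Efficacy, ORR 0.50 | 0.8281 | 0.6960 | 0.6630 |
| Safety, DLT rate 0.25 | 0.9219 | 0.8634 | 0.8257 |
| Joint | 0.7634 | 0.6009 | 0.5474 |

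- ORR 0.60, DLT 0.20: stop 1 − 0.8510 = 14.9%; N = 10 × (1 + 0.9142 + 0.8646 + 0.8510) = 36.3.
- ORR 0.50, DLT 0.25: stop 1 − 0.5474 = 45.3%; N = 10 × (1 + 0.7634 + 0.6009 + 0.5474) = 29.1.
- ORR 0.60, DLT 0.25, same method: 25.1%, N 34.1 (printed 9% and 17%; 38 and 36).

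At DLT rate 0.10 the joint figures are 33.8% for ORR 0.50 (33.7% alone) and 9.4% for ORR 0.60 (9.2% alone). Read the other way, at DLT rate 0.20 Table 10-5 prints 6%, while the joint figure runs from 14.9% (ORR 0.60) to 72.8% (ORR 0.40).

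**Step 4. Dependence**

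With a within-subject correlation (phi) from −0.3 to +0.3, ORR 0.50 with DLT 0.25 gives 42.3% to 47.8% and N 29.8 to 28.6. ORR 0.60 with DLT 0.20 gives 14.1% to 15.3%. The direction does not change.

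**The case against.** **The tables are not miscalculated.** A reader might infer an arithmetic error. Apart from the one average N, there is none: each table is right for its own rule, and one table per rule is a common layout. This stands. What is wrong is the description.

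**The joint risk can be recovered.** A reader might infer that the printed figures conceal it. Under independence, 1 − (1 − a)(1 − b) gives it closely: 9% and 6% give 1 − 0.91 × 0.94 = 14.5%, and 34% and 17% give 1 − 0.66 × 0.83 = 45.2%. This stands for the stopping probability, for a reader who realises that the tables are single-rule. The joint average N cannot be read off in this way.

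**The efficacy rule is discretionary.** The synopsis and Section 10.3.1 leave that stop optional, so a reader who takes both tables as understated in all circumstances goes too far. If the efficacy rule is not applied, Table 10-5 stands. Table 10-3 is still affected, because the synopsis words the safety stop as binding. Section 3.1 lets the review team change dose or schedule instead when its threshold is reached. The two passages need to be reconciled, and the joint figures assume that crossing a boundary stops the trial.

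**The looks may not coincide.** SAP Section 8.1 counts evaluable subjects for efficacy and DLT-evaluable subjects for safety. The DLT window is 42 days from the first pembrolizumab dose (day 15 or 19), the first response scan is at day 64, and safety reviews may be more frequent. The joint figures are exact only for common looks. This limits their precision but does not make the trial-level description true.

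**Part 2 will not proceed.** This stands, and it settles the severity.

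**Conclusion.** The point holds as a labelling gap. The tables are presented as trial-level stopping probabilities, but they are the properties of each rule with the other ignored. With both rules followed at common looks and response independent of DLT, ORR 0.60 with DLT rate 0.20 stops in 15% of trials with an average of 36 subjects, and ORR 0.50 with DLT rate 0.25 stops in 45% with an average of 29. The gap is material when the DLT rate is near the 25% limit and within rounding at 0.10.

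A reader might go further and infer that every printed average N is too high, or that the boundaries are wrong. The documents support neither. At ORR 0.55 the printed 19 is too low, since the joint value with DLT rate 0.20 is about 34; that is a separate error. The boundaries follow from the stated priors and cut-offs.

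Severity is minor: the rules govern Part 2 monitoring only, and Part 2 will not be run.

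**What to change.** 1. In protocol Section 10.3.1 and SAP Section 8.1, describe each table as *probability of crossing this boundary, ignoring the other rule*.
2. Add one grid over true ORR and true DLT rate with the probability of stopping by either rule and the average N. State the assumptions beside it: independence (with a range), common looks at 10, 20 and 30, and whether the efficacy rule is taken as followed.
3. Correct the average sample size at ORR 0.55 in protocol Table 10-3 and SAP Table 3 from 19 to about 35, the value for the efficacy rule alone.

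The cost is a short calculation, one added table and a changed sentence for each existing one. No boundary changes. The stated stopping risk becomes somewhat less favourable near the DLT limit. With Part 2 cancelled, this matters for the record and for any reuse of the design.
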